3.3.4 Exploratory Outcome Measures

The exploratory outcome measures for this study include but are not limited to the following:

BCVA:

- *Difference in mean BCVA change from baseline between the treatment-naïve patients and patients with previous IVT anti-VEGF (differential effect of RO6867461)*
- *Proportion of patients with BCVA 69 letters (20/40 or better) over time*
- *Proportion of patients with BCVA ≥ 84 letters (20/20 or better) over time*

Disease-related exploratory outcome measure:

- Proportion of patients with DR severity improvement from baseline on the ETDRS-DRSS (diabetic retinopathy severity score) at Week 24

Anatomic exploratory outcome measures:

- Change from baseline in macular perfusion and leakage by FFA at Week 12
- Change from baseline in peripheral perfusion and leakage by FFA at Week 24

Durability-related exploratory outcome measures:

- *Time to increase of CST by $\geq 50\mu\text{m}$ and/or loss of ≥ 5 letters of BCVA due to DME compared to values at Week 20*
- *Time to treatment with 0.3 mg ranibizumab after Week 20*

4. MATERIALS AND METHODS

4.1 CENTERS

This is a multicenter study to be conducted in the United States. Additional site(s) in the United States will be included for back-up purposes and may be activated if needed. The site investigators will be qualified ophthalmologists/retinal specialists.

Administrative and Contact Information and List of Investigators are provided separately.

4.2 STUDY POPULATION

4.2.1 Inclusion Criteria

Patients must meet the following criteria for study entry:

Ocular criteria for study eye:

- Macular edema associated with DR defined as macular thickening by spectral domain optical coherence tomography (SD-OCT) involving the center of the macula: CST of $\geq 325\mu\text{m}$ with Spectralis (Heidelberg) at screening (where Spectralis is not available, the following devices and CST thresholds are acceptable: CST $\geq 315\mu\text{m}$ for Cirrus, CST $\geq 315\mu\text{m}$ for Topcon, CST $\geq 295\mu\text{m}$ for Optovue)
- Decreased VA attributable primarily to DME, with BCVA letter score of 73–24 letters (inclusive) on ETDRS-like charts (20/40–20/320 Snellen equivalent) on Day 1
- Clear ocular media and adequate pupillary dilatation to allow acquisition of good quality retinal images to confirm diagnosis

General criteria:

- Diagnosis of diabetes mellitus (DM; Type 1 or Type 2), as defined by the World Health Organization and/or American Diabetes Association
- Able and willing to provide written informed consent and to comply with the study protocol according to International Conference on Harmonisation (ICH) and local regulations. Alternatively, a legally authorized representative must be able to consent for the patient according to ICH and local regulations.

RO6867461—F. Hoffmann-La Roche Ltd
34/Protocol BP30099, Version 3

- Age ≥ 18 years
- For women who are not postmenopausal (i.e. ≥ 12 months of non-therapy-induced amenorrhea, confirmed by FSH, if not on hormone replacement) or surgically sterile (absence of ovaries and/or uterus) agreement to remain abstinent or use combined contraceptive methods that result in a failure rate of $< 1\%$ per year during the treatment period and at least through 4 weeks after last dose.

Abstinence is only acceptable if it is in line with the preferred and usual lifestyle of the patient. Periodic abstinence (e.g., calendar, ovulation, symptothermal, or postovulation methods) and withdrawal are not acceptable methods of contraception.

Examples of contraceptive methods with an expected failure rate of $< 1\%$ per year include male sterilization, hormonal implants, proper use of combined oral or injected hormonal contraceptives, and certain intrauterine devices.

Alternatively, two methods (e.g., two barrier methods such as a condom and a cervical cap) may be combined to achieve a failure rate of $< 1\%$ per year; barrier methods must always be supplemented with the use of a spermicide.

- For men: agreement to use a barrier method of contraception during the treatment period for at least 4 weeks after the last dose of study drug
- Patients must be willing not to participate in any other clinical trial including an investigational medical product (IMP) or device up to completion of the current study.

4.2.2 Exclusion Criteria

Patients who meet any of the following criteria will be excluded from study entry:

Ocular criteria for study eye:

- Any signs of high-risk PDR defined as:
 - any vitreous or pre-retinal hemorrhage
 - NVE $\geq 1/2$ disc area within an area equivalent to the standard mydriatic ETDRS 7- field on clinical examination
 - NVD $\geq 1/3$ disc area on clinical examination
- Any IVT anti-VEGF treatment within 3 months prior to Day 1
- Any panretinal photocoagulation (PRP) treatment prior to Day 1
- Any macular laser photocoagulation within 3 months prior to Day 1
- History of vitreoretinal surgery
- Any IVT or periocular corticosteroid treatment within 3months prior to Day 1. Any history of Iluvien or Ozurdex implants prior to Day 1 will not be permitted
- Any cataract surgery or treatment for complications of cataract surgery with steroids within 3 months prior to Day 1
- History of incisional glaucoma surgery

- Uncontrolled glaucoma (e.g., progressive loss of visual fields or defined as IOP ≥ 25 mmHg despite treatment with anti-glaucoma medication)

Concurrent ocular conditions in the study eye:

- History of rubeosis
- Any current or history of ocular disease other than DME that may confound assessment of the macula or affect central vision (e.g., AMD, retinal vein occlusion, uveitis, angioid streaks, histoplasmosis, active or inactive cytomegalovirus, pathological myopia, retinal detachment, macular traction, macular hole, significant cataract)
- *Any current ocular condition for which, in the opinion of the investigator, visual acuity loss would not improve from resolution of macular edema (e.g., foveal atrophy, pigment abnormalities, dense sub-foveal hard exudates, non-retinal condition)*
- Any active ocular infection on Day 1
- Any active intraocular inflammation (grade trace or above) on Day 1

Characteristics for fellow eye:

- Any anti-VEGF treatment within 7 days prior to Day 1
- Any retinal condition that, in the opinion of the investigator, might require anti-VEGF treatment within 7 days from Day 1

General criteria:

- Any systemic anti-VEGF within 6 months prior to Day 1
- Any major illness or major surgical procedure within 1 month prior to Day 1
- Any febrile illness within 1 week prior to Day 1
- Any stroke or myocardial infarction within 12 months prior to Day 1
- Uncontrolled blood pressure (BP; defined as systolic > 180 mmHg and/or diastolic > 100 mmHg while patient at rest). If a patient's initial reading exceeds these values, a second reading may be taken *either 30 or more minutes later on the same day or on another day during the screening period*. If the patient's BP needs to be controlled by antihypertensive medication, the patient *should be taking the same medication continuously for at least 1 month prior to Day 1*.
- Patients with glycosylated hemoglobin HbA1c $> 12\%$ at screening
- Untreated diabetes mellitus or initiation of oral anti-diabetic medication or insulin within 4 months prior to Day 1 or anticipated change of anti-diabetic medications within the duration of the study
- Renal failure requiring renal transplant, hemodialysis, or peritoneal dialysis within 6 months prior to Day 1 or anticipated to require hemodialysis or peritoneal dialysis at any time during the study

- History of other disease, metabolic dysfunction, physical examination finding, or clinical laboratory finding giving reasonable suspicion of a condition that contraindicated the use of the IMP or that might affect interpretation of the results of the study or renders the patient at high risk for treatment complications in the opinion of the investigator
- For females of childbearing potential, a positive blood pregnancy test
- Lactating female
- Use of systemic corticosteroids within 1 month prior to Day 1
- Any known hypersensitivity to active comparator, fluorescein, any ingredient of the formulation used, dilating eye drops, or any anesthetics and microbial drops used
- Any other restriction accorded to the use of the active comparator
- Any treatment with IMP in the 3 months prior to Day 1

4.3 METHOD OF TREATMENT ASSIGNMENT AND MASKING

4.3.1 Treatment Assignment

After written informed consent has been obtained, all patients will receive a screening number assigned through the interactive voice and web response system (IxRS).

A patient must satisfy all eligibility criteria (see Section 4.2.1 and Section 4.2.2) at the screening or Day 1 visit (as defined for each individual criterion in Section 4.2 and below) prior to randomization and first study treatment (see Section 4.6.7.1). As part of the screening process, FP, FFA, and SD-OCT will be transferred to the central reading center, and a set of images will be evaluated to provide an objective, masked assessment of certain eligibility criteria.

Only one eye will be selected as the study eye. See Section 4.6.7.1 for details.

After all patient eligibility requirements are confirmed on Day 1 visit (see Section 4.2), including:

- Baseline BCVA letter score of 73 to 24 letters (inclusive) in the study eye
- Absence of active intraocular inflammation in the study eye
- Absence of febrile illness within one week prior to Day 1,

the site personnel will contact the IxRS for assignment of a patient identification number (a separate number from the screening number).

Treatment naïve patients will be randomized in a 1:1:1 ratio to one of the arms A, B and C, respectively. Patients previously treated with IVT anti-VEGF will be randomized in a 1:1 ratio to arms A and C.:

- Arm A: 0.3 mg ranibizumab IVT
- Arm B: 1.5 mg RO6867461 IVT

RO6867461—F. Hoffmann-La Roche Ltd
37/Protocol BP30099, Version 3

- Arm C: 6 mg RO6867461 IVT

This study will consist of a treatment period (20 weeks) and an observational period (up to 16 weeks), for a total study length of up to 36 weeks. During the treatment period, the study drug will be administered to the patients on Day 1 and on every 4th week, for a total of 6 injections. During the observational period, patients will be evaluated every 4th week. If during any of these evaluations the patients meet the pre-specified criteria (see Section 4.3.1.1), the patients will receive a single dose of 0.3 mg ranibizumab and exit the study. They will receive a follow up phone call 7 days after the dose of ranibizumab to evaluate any potential adverse events. Otherwise, patients will exit the study once they have completed the observational visit at week 36.

Patients will be randomized on the same day the study treatment is to be initiated (Day 1 visit). After randomization and at each visit with study treatment administration (i.e., Day 1 through week 20), the IxRS will assign the appropriate study treatment kit to be used.

Randomization will be stratified for the factor below:

- Baseline BCVA ETDRS letter score assessed on Day 1 (64 letters or better vs. 63 letters or worse)
- Previous Macular Laser treatment (Yes/No)
- Previous IVT anti-VEGF treatment in study eye (Yes/No)

Randomization with fixed permuted blocks will be used to obtain an approximate *equal allocation* ratio between the different arms within each stratum.

4.3.1.1 Criteria for Treatment with Ranibizumab during Observational Period

At each visit following the last dose of study treatment (week 20 visit), BCVA will be assessed and SD-OCT imaging will be performed (except for week 26 visit).

BCVA and CST values obtained at week 24 will be compared to those obtained at visit week 20. BCVA and CST values obtained at weeks 28, 32 and 36 will be compared to those of week 24.

If the patient meets both of the following criteria the patient should receive a single dose of 0.3 mg ranibizumab and will exit the study:-

- CST increased by $\geq 50 \mu\text{m}$
- BCVA decreased by ≥ 5 letters due to DME

4.3.2 Treatment Administration Procedure

Study drug will be administered IVT. The procedures are detailed in [Appendix 3](#) and the Pharmacy Manual. *Ranibizumab during the observational period should be administered as per local practice.*

At the discretion of the investigator, the sites may use either propacaine- or tetracaine-based ophthalmic drops, subconjunctival injection of lidocaine or lidocaine gel. All efforts should be made to maintain the same anesthetic procedure throughout the study for a given patient, to minimize bias and the risk of unmasking.

At the discretion of the investigator, the patient may self-administer ophthalmic broad-spectrum antimicrobial drops before and/or after study treatment administration.

4.3.3 Masking

This is a double-masked study.

Patients, study site personnel (with the exception of the pharmacist or designated personnel), BCVA examiners, vendors, Central Reading Center personnel, and the Sponsor and its agents (with the exception of drug accountability monitors and as defined in Section 4.3.3) will be masked to study drug assignment.

There *should* be a minimum of two investigators per site to fulfill the masking requirements of this study. At least one investigator will be designated as the assessor physician who will be masked to patients' study drug assignment and will evaluate all ocular assessments. At least one other investigator (and designated, unmasked assistant, as needed) will be designated as the treatment administrator physician who *could* be unmasked to patients' study drug assignment and will administer study treatment (RO6867461, ranibizumab).

If only one investigator is available due to limited staffing resources, study drug administration can also be done by the assessing physician. In that case the treatment administrator physician(s) must not be involved in any aspects of un-masked study drug preparation. The preparation of the study drug must be done by trained staff under strict sterile condition. Detailed instructions for preparation are available in the pharmacy manual.

The Principal Investigator must be masked to the patient's treatment assignment. All roles for each study staff member should be clearly documented in the site delegation log. The delegation log should be signed by the Principal Investigator. *An unmasked personnel cannot switch to a masked role, but a masked personnel can switch to an unmasked role. Any change should be documented in the delegation log.*

In the event an alternate investigator needs to be substituted for an investigator, that alternate physician may assume only one role (i.e., treatment administrator physician or

RO6867461—F. Hoffmann-La Roche Ltd
39/Protocol BP30099, Version 3

Clinical Study Report: RO6867461 - F. Hoffmann-La Roche Ltd
Protocol BP30099 Report Number 1083913

assessor physician) for the duration of the study. The treatment administrator physician(s) performing the *study drug* administration must not divulge study drug assignment to anyone.

The number of unmasked study personnel *should be limited* to ensure the integrity of this masked study. There *should* be no more than five unmasked personnel at an investigative site at one time. Under certain circumstances, the total number of unmasked personnel might be increased after discussion and approval by the Sponsor.

For the duration of the study, the patient study drug assignment will not be unmasked unless required for patient safety.

All study visit assessments, except those at screening, should be performed by masked site personnel only. The treatment administrator physician performing the injection of study drug may also perform *other assessments, including* the post-injection vision testing (finger counting and, if applicable, hand movement and/or light perception).

Unmasking for independent analysis of the relevant biosamples during the conduct of the study will be performed according the Sponsor's internal standard procedures in place, to ensure integrity of the data. The number of Roche representative(s) and delegates unmasked will be kept to the minimum required to address the objective of the biosample analysis.

IMC members (see Section 3.1.3) will be unmasked at the study drug group level. *The IMC agreement will also identify individuals unmasked at the individual patient level for safety analysis and for the purpose of preparing summary data displays for the IMC meeting.* Other Roche Study Management Team members will remain masked throughout the study.

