A mandatory whole blood sample will be taken for DNA extraction from every patient. The DNA may be used to study genes related to DME, DR, and angiogenesis (e.g., VEGFA, VEGFR2, Ang-2, Tie-2, etc.) and the effect on the PK/PD/efficacy/safety of RO6867461. Data arising from this sample will be subject to the same confidentiality as other mandatory blood samples. This specimen will be destroyed up to 2 years after the final closure of the clinical database.

INVESTIGATIONAL MEDICINAL PRODUCT(S)

Test Product: RO6867461

Vials of sterile, colorless to brownish, preservative-free solution of RO6867461 (120 mg/mL) for IVT administration of either 1.5 mg or 6 mg dose every 4 weeks.

Placebo is provided as sterile, colorless to slightly brownish, preservative-free liquid, used only for dilution of RO6867461 drug product to the appropriate clinical dose.

A volume of 50 μ L will be administered by IVT injection for all study drugs tested in this study.

Comparator: ranibizumab

Ranibizumab (nominal content 0.3 mg/0.05 mL) required for completion of this study will be provided by the Sponsor as a solution formulated at 6 mg/mL and supplied as a single-use vial.

The double-masked design is achieved through strict independence of the pharmacist (or designated personnel) and investigators who are preparing and administering study drug, from the assessing investigators and remaining site personnel.

PROCEDURES

Detailed SoA and procedures are tabulated in Appendix 1 of the protocol.

Screening

Patients with CI-DME who are willing to participate in the study and have given informed consent will undergo a thorough screening examination within 4 weeks of study treatment administration. The screening procedures, as outlined in the SoA, will include review of inclusion and exclusion criteria, medical history, physical examination, assessment of vital signs and ECG, serum pregnancy test for females of childbearing potential, and safety laboratory parameters. A predefined set of imaging criteria for eligibility will be confirmed by a Central Reading Center before enrollment.

Treatment Period

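### Protocol 4.3.3 reserves post-screening assessments for masked staff, then lets a possibly unmasked injector do them without limit; slit-lamp grades and adverse event judgements are the outcomes mainly exposed.

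*Protocol*

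**What the plan says.** All of the following is current text.

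- **General rule (Protocol 4.3.3):** "All study visit assessments, except those at screening, should be performed by masked site personnel only".
- **Permission, in the next sentence:** the physician injecting study drug "may also perform *other assessments, including* the post-injection vision testing".
- **Status of that physician (4.3.3):** at least one other investigator "will be designated as the treatment administrator physician who *could* be unmasked to patients' study drug assignment".
- **Assessor (4.3.3):** at least one investigator "will be masked to patients' study drug assignment and will evaluate all ocular assessments".
- **Sites with only one investigator (4.3.3):** the assessor may also inject. "In that case the treatment administrator physician(s) must not be involved in any aspects of un-masked study drug preparation".
- **Synopsis, Investigational Medicinal Products:** masking rests on "strict independence of the pharmacist (or designated personnel) and investigators who are preparing and administering study drug, from the assessing investigators and remaining site personnel".

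Section 4.3.3 also requires a masked Principal Investigator and bars unmasked staff from moving to a masked role. Its opening exempts only the pharmacist or designee from masking among site staff, which does not fit an unmasked injector.

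**The concern.** A site writing its delegation log cannot tell which sentence governs. Read literally, the second sentence lets an injector who knows the assignment grade a slit-lamp examination or judge an adverse event, which the first sentence forbids.

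The outcomes at stake depend on site judgement:

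- Protocol 6.6.6 tabulates intraocular inflammation and vitreous hemorrhage by slit-lamp grade, and under 4.7.1.1 severe inflammation is a reason to stop study drug. The 6-month monkey study in Protocol 1.2.1 found dose-dependent ocular inflammation, so this is a finding that one would want graded without knowledge of arm.
- Seriousness, severity and causality of each adverse event are the investigator's call (Protocol 5.3 and 5.3.4). Severity is part of the safety outcome measures (3.3.1). Causality helps decide whether the sponsor breaks the code for an unexpected serious event (4.3.4) and feeds expedited reporting (5.7).

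**Working it through.** No arithmetic bears on whether the sentences conflict, and the plan gives no figure to reproduce. The check sets the passages side by side, outcome by outcome.

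**Step 1. Do the two sentences conflict?** The first covers every assessment after screening. The second adds a permission for the injector in which vision testing is introduced as one example among others. It carries no closed list and no condition on masking status. Since the injector may be unmasked, some assessments are both forbidden and allowed to the same person.

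**Step 2. Does another sentence settle it?** The assessor sentence assigns ocular assessments to a masked physician, but the later permission cuts across it. The bar on taking part in unmasked preparation is tied to the single-investigator case, so it does not restrict an injector at a site with two. The synopsis points the other way from 4.3.3 altogether: it describes injectors and assessors as separate, whereas 4.3.3 lets one physician do both.

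**Step 3. Which outcomes are exposed?**

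| Outcome | Stated protection | Exposure |
|---|---|---|
| BCVA, including the primary endpoint | Dedicated masked examiner with no other direct-care tasks (4.6.5.2.1) | Protected |
| OCT, angiography and fundus photography readings | Central Reading Center (4.6.5), staff masked (4.3.3) | Protected |
| Slit-lamp and ophthalmoscopy findings | Masked assessor (4.3.3), undercut by the permission | Exposed |
| Adverse event seriousness, severity, causality | The investigator (5.3, 5.3.4); no masked role named | Exposed |
| Attribution of letter loss to DME (4.3.1.1, 3.3.4) | No role named, but the loss itself is measured masked | Marginal |

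**Step 4. At which visits does the permission apply?** It attaches to injection of study drug. Appendix 1 schedules that at Day 1 and Weeks 4, 8, 12, 16 and 20, so 6 visits. Slit-lamp examination is scheduled at all 6. On Day 1 it is a pre-dose baseline, which leaves 6 − 1 = 5 examinations after treatment has begun. The Week 24 to 36 visits, where the exit criteria are applied, have no scheduled study drug.

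**Step 5. How many sites are affected?** The documents give no number of sites with an unmasked injector. All arms receive 50 µL on the same schedule with no sham, so an injector who does not prepare drug has no stated need to know the assignment. The number could be small.

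**The case against.** The best defence is that the sentences can be read together. An injector may be unmasked but need not be. Item 8 of the amendment history explains that, with sham removed, the assessing physician may inject if not involved in preparation. On that reading the general rule still binds, and the permission serves an injector who has stayed masked. This is probably what was meant. It does not remove the point, because the current sentence omits the qualifier that would say so.

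Other objections limit the consequences, and they stand:

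- **Eye examinations.** A reader might infer that these have no protection. They do: the assessor sentence covers them and the Principal Investigator must be masked. The defect is that a later sentence weakens that protection.
- **Time to retreatment.** A reader might infer a serious bias here. The permission does not clearly reach the Week 24 to 36 visits. Exit requires both a CST rise of at least 50 µm and a loss of at least 5 letters, the latter from a masked examiner, and the durability outcomes are exploratory (3.3.4). Some exposure remains. Nobody is named to make the DME attribution, an injector unmasked during treatment cannot become masked again, and one durability outcome joins its two criteria with and/or, so letter loss alone can count.
- **Causality.** A reader might treat attribution as a main safety result. Protocol 3.3.1 lists incidence and severity, and SAP 3.6.1 names no relatedness analysis (the List of Planned Outputs is not available here). SAP 3.6.6 names only BCVA and IOP, although Protocol 6.6.6 does tabulate inflammation grades.

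**Conclusion.** The contradiction is real and sits in consecutive sentences of current text. As written, 4.3.3 permits unmasked grading of inflammation and hemorrhage and unmasked judgement of adverse events, against its own general rule, its assessor sentence and the synopsis.

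The reach is limited to site-judged safety outcomes, with a marginal effect on exploratory durability. It would be wrong to infer that the primary comparison is compromised, since BCVA and central imaging have their own masking. The size of any bias cannot be derived from the documents: it depends on how many sites have an unmasked injector and how many of those use the permission, and neither is stated. The conclusion assumes that sites would apply the sentence as written and not its probable intent. This is a cheap improvement, not a threat to the main result.

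**What to change.** Reconcile the sentences in Protocol 4.3.3 so that:

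1. the wider permission applies only to an administrator who has stayed masked, meaning one not involved in unmasked drug preparation;
2. an unmasked administrator performs only the injection and the immediate post-injection safety checks;
3. ocular examinations, adverse event seriousness, severity and causality, and the attribution of letter loss to DME are made by a masked investigator.

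Then align the synopsis sentence with 4.3.3, including the single-investigator arrangement, and correct the list of masking exemptions at the start of 4.3.3.

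No new staff are needed: 4.3.3 already provides for a masked assessor, and at single-investigator sites that physician stays masked by not preparing drug. No dose or clinical rule changes. The cost is some scheduling flexibility at sites with an unmasked injector. One compromise remains: post-injection IOP, itself a safety measure, could still be taken by an unmasked injector as an immediate check.
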